1. INTRODUCTION

This document outlines the statistical methods to be implemented during the analyses of data collected within the scope of Study ZP4207-21052, entitled “A Phase 3, single-administration open-label trial to assess the efficacy, safety, pharmacokinetics, and pharmacodynamics of dasiglucagon when administered as a rescue therapy for severe hypoglycemia in pediatric patients below 6 years of age with Type 1 Diabetes (T1D)”. The purpose of this SAP is to provide specific guidelines for the statistical analyses. Any deviations from this plan will be documented in the CSR.

2. STUDY DOCUMENTS

The following study documents are used for the preparation of the SAP:

- Protocol, version 6.0, 12 Jul 2024
- Annotated electronic case report form (eCRF), version 6, 14Aug 2024
- Data management plan, version 3, 22 May 2024

3. STUDY OBJECTIVES

The primary study objective is:

- To assess the efficacy of dasiglucagon injection in children < 6 years of age with T1D

Other study objectives are as follows:

- To assess PK of dasiglucagon in children with T1D
- To assess the safety profile of dasiglucagon in children with T1D

4. STUDY DESIGN AND PLAN

This trial will use a single-administration, open-label trial design to assess the ability of a single SC injection of dasiglucagon to increase plasma glucose in pediatric children with T1D with hypoglycemia. A total of 8 children will be included; 4 children receiving a dose of 0.3 mg and 4 children receiving a dose of 0.6 mg. Of the 4 children receiving 0.3 mg, at least 2 children must be below 2 years at screening. The remaining 2 children aged 2 years or above receiving 0.3 mg should preferably be below 4 years at screening. For children receiving the 0.6 mg dose, all must be above 2 years at screening. Before an eligible child is dosed, the dose level (0.6 mg or 0.3 mg) must be confirmed by the sponsor. Each child will be dosed after the safety assessment of the preceding child has been completed and assessed by the Trial Safety Group.

[figure not shown]
The trial will include the following visits (as illustrated in Figure 4-1).

- A screening visit (Visit 1, pre-treatment visit) in the period from Day -50 to Day -29
- A dosing visit (Visit 2), Day 1 (day of single dosing with IMP)
- A Safety follow-up visit (Visit 3) at Day 29 +5 days (the end-of-trial visit)

The primary endpoint of the trial is plasma glucose change from baseline at 30 minutes after IMP injection or at the time of rescue by IV glucose. Pharmacodynamics (PD) i.e., plasma glucose

will be assessed at baseline and 15 and 30 minutes after dosing, while the glucose levels will be monitored by CGM and by a plasma glucose analyzer during the dosing visit (Visit 2). PK will be assessed throughout a 300-minute period at the dosing visit (Visit 2). Safety will be assessed prior to dosing and throughout a 300-minute period after dosing and again at the follow-up visit. All data must be logged in the electronic case report form (eCRF).

Figure 4-1 Trial Design, taken from study protocol.

The schedule of assessments and trial procedures is available in the protocol.

The end of the trial is defined as the date of the last visit of the last patient in the trial. A patient is considered to have completed the trial if he/she has completed all phases of the trial including the last follow-up visit (Visit 3).

5. DETERMINATION OF SAMPLE SIZE

Eight children will be treated in this trial. The number of children is not based on a formal sample size calculation, evaluating the power of the trial, however some considerations have been made with respect to the precision of the estimate of the primary endpoint. In a previous pediatric trial with dasiglucagon (Trial ZP4207-17086), the mean plasma glucose change from baseline at 30 minutes after IMP injection was 96 mg/dL with a standard deviation (SD) of 20 mg/dL in children aged 6 to 11 years. Assuming the variation is the same in children < 6 years

of age, a 95% confidence interval will have a width of ± 25 mg/dL around the mean plasma glucose change with 95% probability, when 8 children are treated.

The power procedure in SAS with the onesamplemeans statement have been applied for the sample size consideration.

6. GENERAL ANALYSIS CONSIDERATIONS

The statistical analyses will be reported using TLFs. The International Council for Harmonisation of Technical Requirements for Pharmaceuticals for Human Use (ICH) numbering convention will be used for all TLFs.

Continuous variables will be summarized by presenting the number of observations, means, SDs, medians, minimums, and maximums. In addition, 95% confidence intervals (based on a *t* distribution if not otherwise stated) will be calculated if appropriate and detailed in the table shells. For logarithm-transformed data (relevant for selected PK summaries), the geometric mean and coefficient of variation % will also be provided.

Categorical variables will be summarized by presenting counts and percentages of subjects in corresponding categories. All possible categories as defined in the CRF should be populated, even if they have zero counts. Percentages for missing values are omitted and do not account for the percent calculation of other categories. Percentages are based on the total category count excluding the missing category if not otherwise mentioned. In certain tables (eg, AEs), the total number of subjects is used as the denominator. Footnotes will specify the percent basis in those cases.

All data collected in this trial and documented in the eCRFs will be presented in data listings. In case of termination of the trial, all data collected up to that time point will be included in the analysis.

All summary tables will be presented for the two treatment groups and total.

Individual subject data obtained from the eCRFs, external vendors, central clinical laboratory, central ECG laboratory, PK data, and any derived data will be presented by subject in data listings.

The analyses described in this plan are considered a priori, in that they have been defined before first patient dosed in the study. Any analyses performed after first patient dosed will be considered post hoc and exploratory. Post hoc analyses will be labeled as such on the output and identified in the CSR.

All analyses and tabulations will be performed using SAS® statistical software, version 9.4 or higher (SAS Institute Inc., Cary, North Carolina, USA). PK and PD analyses will be performed using Phoenix® WinNonlin®, version 8.3.4 or higher (Certara USA, Inc., Princeton, New Jersey, USA). This software was validated by Syneos Health in compliance with US 21 CFR Part 11 Regulation.

All statistical analysis will be performed as per Syneos SOPs.

7. NOTATION OF TREATMENT GROUPS AND VISITS

Notation of Treatment Groups

The following notation of treatment groups will be used throughout the report:

| Full notation (as used in the study protocol) | Notation used throughout all tables, listings, and figures |
|---|--|
| dasiglucagon, 0.6 mg/0.6 mL SC injection | dasiglucagon 0.6mg |
| dasiglucagon, 0.3 mg/0.3mL SC injection | dasiglucagon 0.3mg |

Visit Terminology

| Visit | Notation used throughout all tables, listings, and figures |
|---------------------|--|
| Screening VISIT 1 | Screening |
| Visit 2 (DOSING) | Dosing |
| Visit 3 (FOLLOW-UP) | Follow-up |

Study Days

Study days corresponding to measurements are calculated as:

- Assessment date – date of exposure to treatment + 1 (if assessment date is on or after the date of exposure to treatment).
- Assessment date – date of exposure to treatment (if assessment date is before the date of exposure to treatment).

8. ANALYSIS SETS

For the purposes of analysis, the following analysis sets are defined:

- Safety analysis set (SAF): All patients who were enrolled and received at least 1 dose of IMP.
- Full analysis set (FAS): All patients of the SAF.
- PK analysis set (PAS): All patients with at least one quantifiable plasma concentration.

Note: “Enrolled” requires parent’s/legal guardian’s agreement for the child to participate in a clinical trial following completion of the informed consent process and further that the child is screened and found eligible for the trial.

“Screened” requires a patient completed the informed consent process, regardless of whether the patient is eligible or not.

Data from these patients will be listed.

9. STUDY POPULATION

9.1 Patient Disposition

Patient disposition information will be summarized for all patients. Summaries will include the number of patients screened, enrolled, in each analysis set, completing/discontinuing the study and the primary reason for discontinuation.

9.2 Protocol Deviations

Protocol deviations are collected according to the protocol deviation management plan. Major protocol deviations that could potentially affect the efficacy or safety conclusions of the study will be identified before database lock.

The final determination of major protocol deviations will be made during the data review meeting.

All protocol deviations, including the deviation designation (major or minor), and category will be presented in a data listing. Tables will be created for the SAF for all protocol deviations, summarized by the number of subjects in each deviation designation (major or minor) and category.

Due to the COVID-19 pandemic, the following additional analyses will be necessary. If a protocol deviation occurs, it will be documented if there is a relation to the COVID-19 pandemic. These COVID-19-related protocol deviations will be separately presented in tables as described above. In addition, the COVID-19-related protocol deviations will be listed.

9.3 Eligibility

A listing of subjects not fulfilling at least one eligibility criteria will be created.

9.4 Demographic and Baseline Characteristics

Demographic variables include age on consent date, sex, ethnicity, and race.

Other baseline characteristics include height, weight and BMI.

Descriptive statistics will be presented for age, age group (< 2 years, 2 to < 4 years, 4 to < 6 years), height, weight, weight group (<15kg, >= 15kg) and BMI. Frequency counts and percentages will be presented for sex, ethnicity and race. Demographic and baseline characteristics will be summarized for the SAF.

Time since diagnosis of diabetes (date of informed consent – date of diabetes diagnosis + 1) in months will also be included in this summary, using descriptive statistics. If the day of diabetes diagnosis is not available, the calculation of duration will be based on month and year only, imputing the start day to 1. In case only the year is available, the start day will be imputed to be 1 and the start month will be imputed to be January.

A demographic and baseline characteristics listing will also be provided for the SAF.

9.5 Medical History

The verbatim term of the medical history condition/event will be coded using the Medical Dictionary for Regulatory Activities (MedDRA), version 24.1.

A summary table will be prepared, summarizing the counts for each SOC and PT, ordered by descending order of incidence of SOC and PT.

A listing will be provided for the SAF.

9.6 Prior and Concomitant Medications and Current Diabetes Treatment

Prior and concomitant medication and current diabetes treatment verbatim terms in the eCRFs will be mapped to the WHO Anatomical Therapeutic Chemical (ATC) classification and preferred names using the WHODrug dictionary, Global B3 format, Sep.1.2021 release.

The distinction between prior and concomitant medications is as follows:

- Prior medication are all medications which stopped before the first IMP administration during the study, regardless of start date.
- Concomitant medication is all medication that started prior to the first IMP administration and is still ongoing or stopped at the date of first study drug intake - or medication that started on or after the date of the first IMP administration.
- If the start or stop date is incomplete and the allocation to prior or concomitant is unclear, the medication will be considered concomitant.

Partial dates will be imputed. For details on imputation rules, refer to Appendix A: Presentation of Data and Programming Specifications. Imputed dates are only used for classification of a medication as a prior or concomitant medication; no other calculation, such as durations, will be done.

Prior and concomitant medications and current diabetes treatment will be summarized by WHO ATC class (level 2) and preferred name. These summaries will present the number and percentage of patients using each medication. Patients may have more than 1 medication per ATC class and preferred name. At each level of patient summarization, a patient is counted once if they reported 1 or more medications at that level. Each summary will be ordered by descending order of incidence of ATC class and preferred name.

A listing will be created, listing all prior and concomitant medications as documented on the eCRF. A flag will be included in this listing, identifying which medications are prior and which are concomitant. An additional listing will be produced, listing all data collected on current diabetes treatment, as documented on the eCRF.

10. EFFICACY ANALYSES

The primary efficacy analysis will be based on the FAS.

10.1 Efficacy Variables

The primary efficacy variable is:

- Plasma glucose concentration change from baseline at 30 minutes after IMP injection or at the time of rescue by IV glucose, if before 30 minutes.

The secondary efficacy variable is:

- Plasma glucose concentration change from baseline at 15 minutes after IMP injection or at the time of rescue by IV glucose, if before 15 minutes.

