5.1 Inclusion Criteria

Children are eligible to be enrolled in the trial only if all of the following criteria apply:

Age

1. Child must be < 6 years at the time of screening.

Type of Patient and Disease Characteristics

2. Children who are confirmed as having T1D based on medical history and are receiving daily insulin therapy via insulin pump or MDI.

Informed Consent

- 3. Following receipt of verbal and written information about the trial, the parent(s) or legal guardian of the child must be capable of giving signed informed consent before any trial-related activity is carried out as described in Appendix 1 which includes compliance with the requirements and restrictions listed in the informed consent form (ICF) and in this protocol.
- 4. Ability to adhere to the protocol requirements.

Weight

5. Body weight > 8 kg.

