6.5.2 Rescue Provisions for Hypoglycemia

During insulin-induced hypoglycemia, plasma glucose levels as well as the patient status will be monitored closely throughout the procedure. After administration of IMP (t=0), if their glucose levels become too low, patients may receive post-treatment IV glucose infusion to ameliorate hypoglycemia, as follows:

- The IV glucose infusion should be initiated if a patient experiences escalating symptoms
 of hypoglycemia (eg, start of moderate symptoms of hypoglycemia) at any time during
 the test procedure. Glucose infusion should then be initiated targeting a plasma glucose
 level >90 mg/dL.
- If plasma glucose is <70 mg/dL between t=8 and t=30 minutes, glucose infusion (eg, 1 to 2 mg/kg administered over 5 to 10 seconds) should be initiated to maintain plasma glucose between 70 mg/dL (inclusive) and 90 mg/dL. Pause glucose infusion if plasma glucose is >90 mg/dL.
- If plasma glucose is <90 mg/dL at t≥30 minutes, glucose infusion (eg, 2 to 3 mg/kg administered over 5 to 10 seconds) should be initiated. Pause glucose infusion when plasma glucose is >90 mg/dL.

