8.1.2 Dosing Visit

The dosing visit (Visit 2) will take place 4 to 7 weeks after Visit 1 in order to allow sufficient recovery between blood draws in order to accommodate pediatric volume restrictions. Patients will be admitted to the clinic with their parent(s)/legal guardian(s) in the night before or at early morning of the dosing day (Day 1). The patient's eligibility will be checked.

The following assessments will take place:

- Inclusion/exclusion criteria (prior to the start of the insulin-induced hypoglycemic procedure. Check of exclusion criteria at clinic admission on Visit 2 and changes between screening visit [Visit 1] and Visit 2)
- Body measurements
- Diabetes diagnosis and current diabetes treatment
- Concomitant medications (prior to the start of the insulin-induced hypoglycemic procedure, and during and after the insulin-induced hypoglycemic procedure)
- Exclusion criteria at clinic admission (prior to the start of the insulin-induced hypoglycemic procedure)
- Insulin-induced hypoglycemia
- Physical examination
- Vital signs (prior to the start of the insulin-induced hypoglycemic procedure [within 30 minutes], and at 30, 60 and 300 minutes after dosing. The actual time of the assessment should not deviate from the nominal time by more than ± 10 minutes)
- Local tolerability (at 30, 120, and 300 minutes after dosing. The actual time of the assessment should not deviate from the nominal time by more than \pm 10 minutes)
- AEs

 Plasma dasiglucagon, PK sampling as per Table 6-4. The actual time of blood sampling should not deviate from the nominal time by more than ± 1 minute. Pre-dose is defined as within 2 minutes prior to dosing.

EAL&

- Plasma glucose (PD) sampling as per Table 6-4. The actual time of blood sampling should not deviate from the nominal time by more than ± 1 minute for the collection time points. Pre-dose is defined as within 2 minutes prior to dosing).
- If rescue treatment is required before 30 minutes after dosing, a blood sample for plasma glucose (PD sample) will be collected just before start of rescue treatment. No further plasma glucose (PD sample) samples are required after rescue treatment has been employed.

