10.4 Handling of Dropouts or Missing Data

No imputations will be made for missing values. Summaries will be based on observed data only. For handling of PK concentrations and results BLOQ, please refer to section 0

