12.2 Data Handling

Refer to **Table 12-1** for details on which PD and PK samples to be collected based on body weight at Visit 1 and Visit 2.

Table 12-1 PD (for efficacy) and PK Sampling Based on Body Weight

| Body weight at Visit 2 | Visit 2 | |
|------------------------|------------------------------|---|
| | PD samples to draw | PK samples to draw |
| BW > 10.0 kg | pre-dose 15 min 30 min | pre-dose 10 min 20 min 30 min 40 min 60 min 90 min 140 min 220 min 300 min |
| 10.0 ≥ BW > 9.0 kg | pre-dose 15 min 30 min | pre-dose 10 min 20 min 30 min 40 min 60 min 90 min 140 min 300 min |
| 9.0 ≥ BW > 8.0 kg | pre-dose 30 min | pre-dose 10 min 20 min 30 min 40 min 60 min 90 min 140 min 300 min |

Abbreviations: BW=body weight; PD=pharmacodynamics; PK=pharmacokinetics

The raw plasma concentration data will be handled as follows:

For summary tables and figures for plasma concentrations:

- i.) For all pre-dose samples, the sampling time will be set to zero.
- ii.) For post-dose samples, the planned sampling time will be used in summary tables, and the actual sampling times will be used for all figures of individual concentrations.
- iii.) All concentration values below the Limit of Quantification (BLOQ) will be set to zero.
- iv.) Missing post-dose values will not be replaced.

For determination of PK metrics:

- i.) For all pre-dose samples, the sampling time will be set to zero.
- ii.) For post-dose samples, the actual sampling time will be used.
- iii.) All pre-dose concentration values will be set to zero.
- iv.) Post-dose concentration values BLOQ after T_{max} will be set to missing.
- v.) Missing post-dose values will not be replaced.
- vi.) A concentration that is BLOQ is assigned a value of zero if it occurs in a profile after dosing at time zero and before the first measurable concentration.
- vii.) If a BLOQ value occurs after a measurable concentration in a profile and is followed by a value above the lower limit of quantification, then the BLOQ is treated as missing data, and the time point is ignored in the computations.
- viii.) If a BLOQ value occurs at the end of the collection interval (after the last quantifiable concentration) it is treated as missing data.
- ix.) If two BLOQ values occur in succession after C_{max} , the profile is deemed to have terminated at the first BLOQ value and any subsequent concentrations and time points are omitted from pharmacokinetic calculations.

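### A child of 9.0 kg or less at Visit 2 enters the 15-minute secondary summary only if rescued before 15 minutes, so inclusion depends on the outcome

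*SAP*

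**What the plan says.** - **Endpoint.** SAP 10.1 defines the secondary variable as the change in plasma glucose from baseline "at 15 minutes after IMP injection or at the time of rescue by IV glucose, if before 15 minutes". The Table 14.2.2.1 shell adds that, for a child rescued earlier, the value before rescue is carried forward.
- **Sampling.** Table 12-1 in SAP 12.2 (Table 6-4 in Protocol 6.5.3) gives the lightest band no 15-minute sample: "9.0 ≥ BW > 8.0 kg | pre-dose 30 min". The next band up has one: "10.0 ≥ BW > 9.0 kg | pre-dose 15 min 30 min". Entry requires "Body weight > 8 kg", so no eligible band is lighter.
- **Rescue sample.** When rescue is needed before 30 minutes, Protocol 8.1.2 says that "a blood sample for plasma glucose (PD sample) will be collected just before start of rescue treatment". It makes no exception for weight.
- **Rescue trigger.** Protocol 6.5.2 starts IV glucose "If plasma glucose is <70 mg/dL between t=8 and t=30 minutes", or at any time for escalating symptoms.
- **Missing data.** SAP 10.4 imputes nothing: "Summaries will be based on observed data only".
- **Disclosure.** A footnote in Protocol Section 3 warns that the 15-minute endpoint will be assessed only as far as each child's samples allow. SAP Section 13 describes sampling at 15 and 30 minutes without mentioning the lightest band.

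**The concern.** Each rule is clear alone. Together they make inclusion in the 15-minute summary depend on the result for the lightest children. A light child who responds has no 15-minute value. A light child who does poorly enough to be rescued before 15 minutes has one, and it is likely to be low. The footnote discloses that a sample is missing, but neither document says that the value reappears only after early rescue.

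At stake is the 15-minute mean, above all in the 0.3 mg group. Children under 2 years can receive only that dose, so light children probably fall there, although this is an inference. With four children per dose, one value moves the mean visibly.

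**Working it through.** **The plan's own figure.** The documents give no expected 15-minute mean or SD. The only precision figure concerns the primary endpoint: a 95% interval of ±25 mg/dL with 95% probability at n = 8 and SD 20 (SAP Section 5). It reproduces. The half-width at SD 20 is 2.365 × 20/√8 = 16.7, and P(half-width ≤ 25) = 0.971 at n = 8 against 0.910 at n = 7. It does not enter this point.

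**Step 1: where the 15-minute value comes from.**

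| Visit 2 weight | Not rescued by 30 min | Rescued before 15 min | Rescued at 15–30 min |
|---|---|---|---|
| Above 9.0 kg | 15-min sample | pre-rescue sample | 15-min sample |
| Above 8.0 to 9.0 kg | missing | pre-rescue sample | missing |

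In the lightest band, as planned, the value is observed with probability 1 after rescue before 15 minutes and probability 0 otherwise. Above 9.0 kg it is always observed.

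**Step 2: direction.** Before dosing, the analyzer must read at least 70 and below 90 mg/dL (Protocol 6.5.1). A glucose-triggered rescue means a value below 70. If laboratory and analyzer agree, the change is negative: between just under 0 and about −20 for a value just below the trigger. A symptom-triggered value need not be below 70.

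**Step 3: size in one realised sample.** Let *a* be the change in a child not rescued early and *b* the change in one rescued early. Take four children at 0.3 mg, two of them light, one of those rescued early.

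- All four counted: (3a + b)/4. Plan: (2a + b)/3. Shortfall: (a − b)/12.
- a = 50, b = −10: plan (50 + 50 − 10)/3 = 30, all four (150 − 10)/4 = 35, shortfall 5 mg/dL.
- a from 20 to 60 and b from 0 to −20: shortfall from 20/12 = 1.7 to 80/12 = 6.7 mg/dL.
- Total column, n = 7 instead of 8: shortfall (a − b)/56, or 0.4 to 1.4 mg/dL.
- Three light children of four, one rescued early, a = 50, b = −10: plan (50 − 10)/2 = 20 against 35.
- Neither of two light children rescued early: both drop out (n = 2 of 4), with no shift if response is alike across weights.
- Every light child rescued early: all four are observed, so that sample shows no shortfall.

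**Step 4: average over repetitions.** Assume that the probability *p* of rescue before 15 minutes and the changes *a* and *b* do not depend on weight. The true mean is a − p(a − b). With two light children of four,

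bias = −(a − b)(1 − p)[2p(1 − p)/3 + p²/2].

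For p = 10%, a = 50, b = −10: the true mean is 44, the bias is −60 × 0.9 × (0.060 + 0.005) = −3.5, and the plan averages about 40.5. With p = 5% the bias is −60 × 0.95 × 0.0329 = −1.9; with p = 20% it is −60 × 0.8 × 0.1267 = −6.1. With one light child of four it is −(a − b)p(1 − p)/4, or −1.35 at p = 10%. A summary restricted to children above 9.0 kg has expectation 44 and no bias. The values of p, a, b and the number of light children are all assumptions.

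**The case against.** The strongest reply is that this may never happen. Neither document plans any number of children at or below 9.0 kg, and age below 2 years is only preferred in the protocol. The glucose trigger opens at 8 minutes, so only minutes 8 to 15 and symptom-led rescues count. This stands and limits the point. A reader might infer that the 15-minute result is biased downward by construction, but the documents support only a conditional statement.

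Second, a reader might infer that nobody could detect the effect. That goes too far. Table 14.2.2.1 prints n, minimum, maximum and the carry-forward footnote, Table 14.3.5.1 gives rescue and time to first IV glucose by dose, and Listing 16.2.6.1 shows each child's values. These outputs would expose an affected child, but only to someone who pieces them together; the baseline weight groups split at 15 kg and do not show the band. Table 14.2.3.2, which leaves out rescued children, is no correction, since it holds no light child at 15 minutes.

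Third, restricting the summary to children above 9.0 kg can do worse in a given sample. In the main example it gives 50 against 35 for all four, an error of +15, while the plan errs by −5. The arithmetic is right, but it conditions on a light child having been rescued. Before the outcomes are known, the weight-defined rule is unbiased under equal rescue risk and the planned rule is not. What stands is that the restriction removes a failure from the summary, so that child must be shown elsewhere.

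**Conclusion.** The point holds in conditional form. If a child of 9.0 kg or less at Visit 2 is dosed, the 15-minute endpoint is observed only after rescue before 15 minutes. Inclusion in Table 14.2.2.1 then depends on the outcome, and early rescue in this band biases the mean downward. The realised shortfall is 1.7 to 6.7 mg/dL in the 0.3 mg column for one early rescue among two light children, under the assumed changes. The bias is zero if no such child is dosed or none is rescued before 15 minutes.

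Two larger readings should be resisted. The 30-minute primary endpoint is not affected, because that sample is kept in every weight band. Nor is a dose decision by age shown to rest on this table: Protocol 4.3 says that the results will inform the dose or doses for children under 6 years, without naming age bands or the 15-minute endpoint, which is secondary and descriptive and has no planned confidence interval. This is a cheap improvement, not a serious flaw.

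**What to change.** In SAP 10.1 and 11.2 and the Table 14.2.2.1 shell:

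1. State that the 15-minute endpoint is not evaluable by schedule at a Visit 2 weight of 9.0 kg or less.
2. Present the main 15-minute summary for children above 9.0 kg at Visit 2, whatever their rescue status.
3. Keep the currently planned full-analysis-set row beside it, with n by weight band and rescue status.
4. Show each child of 9.0 kg or less individually under the table, including any rescue, its time and the pre-rescue value, so that no failure is hidden.

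An on-site analyzer reading near 15 minutes is a tempting substitute. It should be left out unless a time window is stated in advance. Analyzer checks become sparser once glucose reaches 110 mg/dL and are reduced at low weight (Protocol 6.5.1), so a fast responder may have no reading near 15 minutes. The analyzer is also a different instrument from the laboratory assay.

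The cost is SAP and shell wording only, with no extra blood and no change in trial procedures. The downside is that the main 15-minute summary covers fewer children, does not describe the lightest band, and would look more favourable if a light child were rescued early. The retained row and the individual display offset that. If a child has already been dosed, SAP Section 6 would label the added summary post hoc.
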